#### Screening/ Baseline Assessments:

After the subject has voluntarily signed and dated the informed consent document, the subject will be considered enrolled in the trial. If a subject does not sign the informed consent document, then no further screening procedures for the Valiant Evo International Clinical Trial will occur.

Collection of screening and baseline information will take place only after the subject has given voluntary, documented informed consent and will include the following:

- Subject demographics
- Medical history
- Current health status
- Risk factors
- ASA Physical Status Classification
- EQ-5D Questionnaire

Baseline CT/MRI images will be reviewed by the investigator to confirm eligibility. The imaging will also be sent to a core lab for analysis. An Independent Physician Reviewer (IPR) will review the screening CT/MRI images to assess the anatomical inclusion/exclusion requirements and confirm subject eligibility. Approval by the IPR must be obtained prior to a subject's actual inclusion in the study. The decision of the IPR will be communicated to the investigational site by the Sponsor. Those subjects who sign and date the Informed Consent, meet all study eligibility criteria, and are approved by the IPR will be eligible for inclusion in the study. Subjects that are not approved by the IPR are considered screen failures and will not be followed per study protocol. However, investigators will be requested to enter safety information in the eCRF **from date of point of enrolment until date of screen failure**. Full IPR review process will be documented in a separate document.

Screen failures will be documented on the Screening, Enrollment and Inclusion log and the reason for screen failure will be documented on the screening eCRF.

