#### L.3.3.2 Subject accountability

Subjects already enrolled and willing to extend their follow-up from 12 to 60 months are to be re-consented. Re-consenting is to occur at or prior to the 12-month follow-up visit. Enrolled subjects who decline to continue to participate in follow-up beyond 12-months shall exit the study upon the completion of their 12-month visit.

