At enrollment, those subjects who sign and date the informed consent document, meet all of the study eligibility criteria, and are approved by the IPR will be eligible for inclusion into the Valiant Evo US Clinical Trial. The subject will only be considered enrolled when arterial access is established and an attempt to introduce the Valiant Evo Thoracic Stent Graft is made. A single, primary stent graft may be used by itself if its size is sufficient to provide the desired coverage. Alternatively, it may be used in combination with additional stent graft sections that increases the graft length distally or proximally to the primary section.

The Valiant Evo Global Clinical program will be conducted under both the Valiant Evo US Clinical Trial protocol and Valiant Evo International Clinical Trial protocol, and will enroll up to 37 sites worldwide. Inclusion will be halted at sites that reach the 20% inclusion cap. There will be no minimum number of subjects for a single investigational site. Globally, a total of 100 subjects will be concurrently enrolled in the United States and outside the United States to support the primary endpoints. Up to 50% of subject data used to support PMA approval may come from subjects enrolled at sites outside of the US under the Valiant Evo International Clinical Trial protocol.

The primary endpoint analysis will be completed upon 87 evaluable subjects reaching the 30 day endpoint. The data obtained from these 87 evaluable subjects will be used to support PMA-s Approval of the Valiant Evo Thoracic Stent Graft System and to support any other future Medtronic submissions to regulatory bodies.

Subjects enrolled under the Valiant Evo US Clinical Trial require follow-up evaluations at the following time points:

- 1 month following the index procedure (30 ± 15 days)
- 6 months following the index procedure (183 ± 30 days)
- 12 months following the index procedure (365 ±60 days)
- 24 months following the index procedure (730 ±60 days)
- 36 months following the index procedure (1095 ±60 days)

- 48 months following the index procedure (1460 ±60 days)
- 60 months following the index procedure (1825 ±60 days)

Note that the 6-month follow up is not mandatory for subjects enrolled under the Valiant Evo International Clinical Trial protocol. Available 6-month follow-up data from the international trial will be used for analysis.

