Subjects will be followed until the last subject enrolled has completed the 1 year follow-up visit or until PMA approval is obtained in the US (whatever is later), however, Medtronic will work with FDA to determine if longer term follow after PMA approval is required. A post-approval analysis of 1-year Major Device Event (MDE) rate is planned.

6. Determination of Sample Size

One hundred (100) enrolled subjects will ensure 87 evaluable subjects at 30 days. The primary endpoint analysis will be completed upon 87 evaluable subjects reaching the 30 day endpoint. Based on Valor II study results, Valiant Evo is expected to perform similarly and have 6% of MDE combined with access and/or deployment failures at 30 days. The sample size of 87 evaluable subjects will provide 85% statistical power for the study hypothesis. The type I error is controlled at the one-sided 0.025 level.

Table 1: Power Analysis

True rate of MDEs combined with access and/or deployment failures at 30 day with Valiant Evo	6%
Performance Goal	16%
Significance level	0.025
Statistical test	One-sided binomial test
Evaluable sample size	n=87
Enrollment	Minimum of 100 subjects enrolled to ensure 87 evaluable subjects
Statistical power from the 87 evaluable subjects	85%

One hundred (100) enrolled subjects will also ensure 63 evaluable subjects at 1-year on MDE rate for the post-approval analysis. The VALOR II study with the Valiant stent graft system enrolled 160 patients with DTAA and was assessed through 12 months for purposes of PMA (P100040) approval. Through 1-year post-

treatment, the rate of MDEs combined with access and/or deployment failures was 7.1% (11/153) (Medtronic internal data using the Valiant Evo proposed definition). Therefore, for the purpose of post approval analysis, the rate of MDEs combined with access and deployment failures at 1-year with Valiant Evo is estimated to be 7.1% (refer to Table 22 below for power analysis assumptions).

Table 2: Power Analysis for Post-approval Analysis of 1-year Endpoint

Estimated rate of MDEs combined with access and/or deployment failures at 1 year with Valiant Evo	7.1%
Performance Goal (PG) at 1-year	20%
Significance level	0.05
Statistical test	One-sided binomial test
Evaluable sample size	N = 63 at 1 year
Enrollment	IDE cohort will enroll a minimum of 100 subjects and is expected to have a minimum of 63 evaluable subjects at 1-year follow up.

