7.2. General Methodology

In general, qualitative parameters will be described by their distribution frequencies; quantitative parameters will be described by their mean, standard deviation, minimum, maximum, median, and number of subjects with assessable data.

For events such as adverse events (AE), deaths and secondary procedures, that can occur or are observed at any time during the study, no time window will be applied. For such events, an event that occurs “within 1 month or 30 days” is an event that takes place between Days 0 to 30, inclusive. Similarly, an event that occurs “within 12 months or 365 days” is an event occurring between Day 0 to Day 365, inclusive. Date of event onset will be used to determine when the event occurred. Day 0 is referring to the day of index procedure.

For image-based assessments, such as stent-graft endoleak, patency, and other observations, the following time windows will be applied for by-visit data summaries:

Table 3: Time Windows for Statistical Analyses

Study Visit	Target Day	Time Window
Implant	Day 0	Day 0
1 Month	Day 30	1 – 90 days
6 Months	Day 183	91 – 304 days
12 Months	Day 365	305 – 548 days
24 Months	Day 730	549 – 913 days
36 Months	Day 1095	914 – 1278 days
48 Months	Day 1460	1279 – 1643 Days
60 Months	Day 1825	1644 – 2009 days

Unless otherwise specified, if different type of images are used and have different finding in the same time window, the imaging technique and sensitivity matrix (CIP Appendix L.3, also see Table 4 below) will be applied. Finding from higher visibility image will be used for analysis. If there are two or more assessments in the same time window, then the assessment closest to the target day will be used in the analysis of event rate at a given time point.

Table 4: Imaging Matrix

Anatomy/Stent Graft Issue Detected	CT with contrast	CT without contrast	MRI with contrast	MRI without contrast	Angiogram/, Aortogram, and Arteriogram
Diameter and Length	1	2	1	2	3
Stent graft migration	1	2	1	2	2-3
Stent graft fracture	2	3	2	3	2-3
Stent graft kinking	2	3	2	3	2-3
Collapse of stent graft	2	3	2	3	2-3
Stent graft twisting	2	3	2	3	2-3
Stent graft patency	1	4	1	4	2-3
Endoleaks	1	4	1	4	2-3
False lumen perfusion	1	4	1	4	2-3
Occlusion	1	4	1	4	2-3
Stenosis	1	4	1	4	2-3
Stent Graft Fabric Defect	1	4	1	4	2-3
1= Highly visible 2 = visible 3 = Not very visible (potential artifacts) 4 = Invisible					

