7.4. Handling of Missing Data and Dropouts

During statistical analysis, imputation of missing data will not be performed except for data related to the onset date of an adverse event or a death. In cases where the onset date of an event or a death is incomplete and unresolvable via data query, the 15th day of the known month or July 1st of the known year will be used.

Sensitivity analysis using tipping point method may be performed, as needed, to assess the impact of missing data for the primary endpoint.

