7.11. Health Outcomes Analyses

Health-related quality of life outcomes will be assessed at all scheduled follow-up visits using the EQ-5D questionnaire. For each dimension of EQ-5D score, a frequency table will be presented. For visual analogue scale score, EQ-5D Index and change from baseline in EQ-5D Index, number of subjects with known value, mean, standard deviation, median, minimum and maximum will be reported. The scoring algorithm by Shaw JW *et al* (2004) will be used to compute the US preference-weighted index score.

8. Validation Requirements

Level I validation is required for each computer programmed table and listing used in the PMA and PMA-s submissions.

9. References

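### SAP 7.11 gives a change from baseline for the EQ-5D Index but only level summaries for the visual analogue score, although the set of subjects who answer differs between visits by design.

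*SAP*

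**What the plan says.** SAP 7.11 states: "Health-related quality of life outcomes will be assessed at all scheduled follow-up visits using the EQ-5D questionnaire". It then names what is summarised: "For visual analogue scale score, EQ-5D Index and change from baseline in EQ-5D Index, number of subjects with known value, mean, standard deviation", followed by median, minimum and maximum. Change from baseline is attached to the Index and not to the VAS score.

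No other section supplies the missing change:

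- SAP 7.2: "quantitative parameters will be described by their mean, standard deviation, minimum, maximum, median, and number of subjects with assessable data". This is a rule for levels, with no paired analysis. Protocol H.1 says the same in substance.
- SAP 7.4: "imputation of missing data will not be performed except for data related to the onset date of an adverse event or a death". The optional tipping-point analysis there covers the primary endpoint only.

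The plan also fixes who is due to answer at each visit:

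- **6 months.** SAP 5: "Note that the 6-month follow up is not mandatory for subjects enrolled under the Valiant Evo International Clinical Trial protocol". Available International data at 6 months will be used, but Protocol Tables F-2 and L-2 schedule no EQ-5D then.
- **After 30 days.** Under Protocol F.2.2 and F.2.4, International subjects with treatment failure or conversion to open repair pass to standard of care after the 30-day follow-up, or after conversion if that comes later. Serious adverse events are still recorded for them.
- **After 12 months.** Protocol L.3.3.2: "Enrolled subjects who decline to continue to participate in follow-up beyond 12-months shall exit the study". This concerns International subjects. SAP 5 schedules visits for US subjects out to 60 months.

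The baseline value exists: Protocol F.1 lists the "EQ-5D Questionnaire" among the screening and baseline assessments.

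**The concern.** A table of VAS summaries at baseline, 1, 6, 12 months and later invites the reader to look along the row for a trend. If different subjects stand behind each entry, the row mixes true change with change in who is being averaged. The mean can move at 6 months and return at 12, or drift upward as sicker subjects leave, without any subject's score changing. The count in each cell shows that the denominator changed but does not correct for it.

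The Index has a partial safeguard in the same sentence, because its change from baseline compares each subject with himself or herself. The VAS score has none. What is at stake is the reading of one descriptive quality-of-life outcome. No test or decision rule uses it.

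**Working it through.** **Plan's own figure.** The documents give no VAS mean, standard deviation or completion rate, so there is no EQ-5D figure to reproduce. The one borrowed number is 63 of 100 at 1 year. SAP 6 says: "One hundred (100) enrolled subjects will also ensure 63 evaluable subjects at 1-year on MDE rate". That number belongs to the power analysis for major device effects (MDEs) combined with access and deployment failures. An exact one-sided binomial test with n = 63, performance goal 20% and true rate 7.1% rejects at 7 or fewer events, with type I error 0.047 and power 0.923. This matches the stated 92%. So 63 is a sound planning floor for that endpoint, but it is not an EQ-5D completion rate.

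**Formula.** Suppose no subject's score changes. Let *d* be the share of subjects who do not answer at a visit, and *G* the baseline mean of those who answer minus that of those who do not. The mean of all subjects is (1 − *d*) × answerers + *d* × non-answerers. The visit mean is the answerers' mean alone, so

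spurious shift = *d* × *G*.

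If the absent subjects score higher, the shift has the opposite sign.

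**Inputs**

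- 100 subjects in total (SAP 5 and 6).
- 47 International subjects (Protocol C.7). The 53 US subjects are derived as 100 − 47; neither document states that number.
- *G* = 5 to 10 VAS points: assumed.
- One table pooled over both trials: assumed. SAP 7.3 presumes poolability, and SAP 7.11 does not call for separate EQ-5D tables.

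**6 months, no International subject answers (upper case).** *d* = 47/100 = 0.47, and *G* is the gap between trials.

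- 0.47 × 5 = 2.35
- 0.47 × 10 = 4.70

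**6 months, half of the International subjects answer (assumed).** Their share falls from 0.47 to 23.5/(53 + 23.5) = 0.307, a drop of 0.163.

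- 0.163 × 5 = 0.8
- 0.163 × 10 = 1.6

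**1 year, 63 of 100 answer (proxy).** *d* = 37/100 = 0.37.

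- 0.37 × 5 = 1.85
- 0.37 × 10 = 3.70

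**30 days, 87 of 100 answer.** This is the SAP 6 evaluable number for the primary endpoint, again a proxy. *d* = 0.13.

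- 0.13 × 5 = 0.65
- 0.13 × 10 = 1.30

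**With a paired change.** If no subject changes, every within-subject difference is zero and so is their mean, whoever answers. The *d* × *G* term disappears. What remains is selection on the change itself: if those whose health worsens stop answering, the mean change among responders is still too favourable.

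**The case against.** EQ-5D sits under additional observations in Protocol C.2.3, outside the primary and secondary endpoint lists. Protocol C.3 and H.1 make all endpoints descriptive, and no VAS comparison between visits, test or claim is planned. SAP 7.11 already offers a within-subject quality-of-life measure through the Index. All of this stands and limits the weight of the point. It does not remove it. The Index is scored with US preference weights for all subjects, including those treated outside the US, while the VAS score is the summary that does not use those weights.

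A reader might infer several stronger things that the documents do not support:

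- *That only means are reported.* Counts, standard deviations, medians, minima and maxima are planned too.
- *That from 24 months the only subjects left are re-consented International ones.* Re-consent limits the International subset; the US schedule runs to 60 months.
- *That the plan expects 37% of EQ-5D forms to be missing at 1 year.* The 63 is a minimum for the MDE analysis, whose event-free denominator is defined in SAP Table 5 by time in study.
- *That no International subject can contribute at 6 months.* SAP 5 uses available data, so the full 0.47 share is an upper case. Still, what Protocol F.3 anticipates at 6 months is interim imaging, not a questionnaire.
- *That the Index is fully protected.* Its mean change at each visit also rests on whoever answered. Pairing cancels baseline differences only.

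**Conclusion.** The point holds in a limited form. SAP 7.11 plans within-subject change for the Index and omits it for the VAS score, nothing elsewhere fills the gap, and the responding set changes by design. Differences between VAS summaries at different visits can therefore partly reflect who answered.

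For assumed gaps of 5 to 10 points, the spurious shift is at most 2.4 to 4.7 points at 6 months and about 1.9 to 3.7 points at 1 year. The first rests on a 53/47 split, no International responders and a pooled table. The second rests on the MDE floor as a stand-in for EQ-5D completion. Neither is a prediction: the documents give no VAS data, and the sign depends on who is absent.

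The outcome is descriptive and supplementary. This is a minor improvement, not a flaw that threatens any conclusion of the trial.

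**What to change.** In the SAP 7.11 list, add *and change from baseline in visual analogue scale score*, computed at each visit in subjects who have both the baseline and the visit value. Keep the existing level summary beside it, and show the baseline mean of the subjects contributing at that visit. A short note should say that the paired change removes baseline case-mix differences but not selection by death or drop-out.

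The cost is one phrase in the SAP and a few table rows. No new data are needed, because the planned Index change already requires the baseline questionnaire.
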